8.4 Randomisation Procedure

The King's Clinical Trials Unit will oversee randomisation. This will be a secure password-protected, web-accessed system. The system will generate an email message on allocation.

Participants will be stratified by the following factors:

- (a) Site (trust and city)
- (b) Current (last 28 days) drug injecting status (yes/no)

Justification for these stratification factors is as follows: (a) site is required for the random-effects model; (b) it is expected that there will be relatively poorer outcome among participants who are drug injectors. The randomisation procedure will use stratified random blocks of varying size to ensure even allocation.

Only study site staff authorised by the trial manager will be given login details to the randomisation system. Authorised staff will be allocated a username and password for the randomization system. Prior to randomisation the site needs to ensure there is capacity for the XR-Bup or Bup/Met for each patient.

Once a patient has consented and it is confirmed that all potential medication is in place within the next 7 days, all baseline data collected and eligibility confirmed, the staff member will log into the randomization system (www.ctu.co.uk). The “help” section of the system has video demonstrations to aid new staff in using the system. Once randomized, the system automatically generates confirmation emails to key staff, with or without treatment allocation information, depending on their role in the study. EXPO is an open-label (unblinded) trial, so there is no emergency code break.

8.5 Withdrawal of participants

Participants have the right to withdraw from the study at any time for any reason. The investigator also has the right to withdraw patients from the study drug in the event of AE, SAE, SUSAR, or other reasons. Upon withdrawal from the study the patient will be asked to research measures (with a minimum to enable capture of the primary outcome measure [i.e. TLFB and UDS] and also craving measures). It is understood by all concerned that an excessive rate of withdrawals can render the study uninterpretable; therefore, unnecessary withdrawal of patients should be avoided. Participants who wish to withdraw from EXPO will be asked to confirm whether they are still willing to provide data. Should a patient decide to withdraw from the study, all efforts will be made to report the reason for withdrawal as thoroughly as possible.

The Investigator will maintain a record of all patients who discontinue from the trial prior to completion; the reason(s) for trial discontinuation will be documented. If a patient chooses to withdraw from the trial, the Investigator should make a reasonable attempt to obtain and record the reason(s) for withdrawal, if possible, although the patient is not obligated to provide such a reason.

8.6 End of Trial Definition

The end of the trial will be deemed to occur after database lock (following completion of monitoring of the last patient last visit undergoing the EXPO trial).

9. Trial Procedures

9.1 By visit

The following standardised instruments will be administered during the study:

Urine drug screen (UDS; detection sensitivity: opiates: 2000ng/ml; cocaine and benzodiazepines: 300 ng/ml; window of detection: 72 hours; UDS procedure conducted each visit). A tamper-proof, instant result, immunoassay device (e.g. E-Z Split Key Cup; www.concateno.com) will screen for recent use of opioids, cocaine and benzodiazepines. The device uses a control line and a temperature sensor (required range: 92°-96 °F) to indicate that a valid test has been done. The UDS product for the study also includes measurement of Bup and Met (providing a proxy indicator of medication adherence) and also (meth)amphetamine and cannabis (for description and exploratory analysis).

* **Structured clinical interview for DSM-5 disorders – research version** (SCID-5-RV [34]). The SCID-5-RV contains a checklist of 11 symptoms (presence or absence) to diagnose the severity of current OUD (mild: 2–3 symptoms; moderate: 4–5; severe: ≥ 6). The American Psychiatric Association's definition for early OUD remission will be applied at 3-month follow-up (i.e. without substance use disorder criteria [except] craving, using the “on maintenance therapy” specifier as appropriate).

Alcohol - Quantity, Frequency and Maximum Consumption (ALC-QFM) This information will be recorded using an adapted version of the **Treatment Outcomes Profile** (TOP [54]). The TOP is the standard national instrument for monitoring the outcomes of public substance use disorder treatment services in England.

Time-Line Follow-Back (TLFB) interview for heroin, cocaine and benzodiazepine recorded for each day whether the participant reports using or not using these drugs. The TLFB, calendar-prompt interview will be adapted from the TOP.

Montreal Cognitive Assessment (MoCA; [35]. The MoCA is a brief screening instrument for mild cognitive impairment and assesses attention, concentration, working memory, visuo-constructional skills, and conceptual thinking. A score of ≥ 26 is considered to reflect normal range functioning. An alternate version of the MoCA will be used at follow-up to decrease the risk of learning effects. The MoCa will be completed on 2 visits: baseline (version 7.1) and study week 12 (version 7.2).

***Addiction Dimensions for Assessment and Personalised Treatment** (ADAPT [53]). The ADAPT is a clinician completed 14-item instrument used for drug addiction treatment planning and outcome evaluation with three-subscales: opioid addiction severity, coexisting health and social problems, and recovery strengths.

***Clinical Global Impression** (CGI-S and I; [36]). The CGI is a single item clinician assessment of disorder severity and improvement.

Craving Experience Questionnaire (CEQ-F [frequency] [56]). The CEQ-F will be completed for opioids (CEQ-F[H] and cocaine (CEQ-F[C]). This scale has a 14-day recall period and captures intensity, imagery, and intrusiveness aspects of drug craving.

Visual analogue scale of maximum need (VAS-N[H/C] and want (VAS-W[H/C]). These single item (0-100) rating scales have a recall period of the past 14 days.

Difficulties in Emotion Regulation Scale – Short Form (DERS-SF; [37]). The DERS The DERS is an 18 item self-report scale which records current emotional dysregulation in six subscales: non-acceptance, goals, impulse, aware, strategies and clarity.

QIDS-SR ([39]) The QIDS-SR is a brief scale which assesses the frequency of depressive symptoms during in past two weeks.

Work and Social Adjustment Scale (WSAS; [38]). The WSAS is a 5-item scale which records the extent of social functioning impairment perceived to be caused by OUD in the past two weeks.

Service User Recovery Evaluation (SURE; [6]). The SURE is a patient-reported outcome measure and is a multi-dimensional measure of perceived recovery status.

Patient reported outcome measure - Status (PRO-S and I). The PRO-S is a single 7-point item assessment of the extent to which the participant perceives the severity of their opioid-related problems at baseline and at follow-up.

EQ-5D-5L ([39])The EQ-5D-5L is a brief generic scale which captures health status on five dimensions: mobility, self-care, usual activities, pain/discomfort, anxiety/depression, and with a 20cm vertical visual analogue scale. These responses generate health profiles from which health utilities can be calculated for economic evaluations.

Alcohol and Drug Service Use Schedule (ADSUS). The ADSUS is a well-developed structured patient interview that records use of health, social, welfare and criminal justice services and crime. The ADSUS was successfully used in the ARC trial.

Keyworker Contact Form (KCF). The KCF records the clinical team's direct and indirect time working on EXPO.

The Opioid Substitution Treatment Quality of Life scale (OSTQOL; [40]). The OSTQOL is a 38-item instrument assessing quality of life specific to patients in opioid substitution therapy across 6 subscales; personal development, mental distress, social contacts, material well-being, opioid substitution treatment, and discrimination.

Patient Health Questionnaire- 15 (PHQ-15; [41]). The PHQ-15 is a self-administered somatic symptoms subscale which screens for 15 somatic symptoms that account for more than 90% of the physical complaints reported in the outpatient setting (exclusive of self-limited upper respiratory symptoms).

Patient Health Questionnaire- 4 (PHQ-4; [42]). The PHQ- 4 is a 4-item inventory, rated on a 4-point Likert-type scale. Its purpose is to allow for very brief and accurate measurement of depression and anxiety.

*** The CI/ PI is able to delegate the administration of these instruments to a suitably trained health care professional at all visits subsequent to the baseline/screening assessment.**

9.1.2 Optional Consents

Week 24 onwards. Participants randomised to XR-Bup can continue to receive monthly injections as detailed in section 6.3 until the date the last participant is randomised plus 9 months. The Trial Manager will inform study sites when this date is approaching. At week 24 complete all research measures as detailed in the week 24 summary. Prior to the 7th injection at week 24 the continuing XR-Bup consent form is to be completed and pregnancy test recorded as negative. Following week 24, LFT to be taken approximately every 6 months or as clinically indicated. Conmeds and Adverse Events to be recorded at each visit that XR-Bup is administered.

Exit Interview. To be conducted at the South London, Newcastle, West Midlands and Tayside sites with XR-Bup participants only. An additional consent will be taken from the participant to undertake a semi structured, topic guided interview detailing their drug use and experiences whilst being on the trial (based on the ADAPT). This interview can take place at the same time as the week 24 visit or scheduled for a time convenient to the participant and interviewer. Participants will be reimbursed an additional £20 for their time in taking part in the interview. Researchers are to follow the EXPO Exit Interview Schedule as a topic guide, but the interview is designed to be semi structured. Where possible, have the participant to do a face-to-face interview when they are coming in for their injection (week 28 etc) if they are continuing onto the extension phase or at a time convenient to them at a time after their week 24 visit. If a face-to-face interview is not possible interviews can be recorded over the telephone; with the call on speaker and recorded using the audio recorder. When starting the interview, the participant should be reminded that the interview will be recorded, the length of time it may last, arrangements for payment and that they can withdraw from the interview at any time. Audio recordings should be recorded on trust approved audio recorders, the interviewer who conducted the interview is responsible for transcribing the interviews verbatim, naming the document with the participant number for the trial. Original audio file recordings are to remain at the site, securely stored electronically as per local policy unless a Data Share Agreement is in place with the study sponsor. Transcripts with no personal identifiable information of the recordings will be sent to the study sponsor periodically upon request.

Bup/Met +PSI Interview. To be conducted at the South London site only with approx. 30 participants who are randomised to the Bup/Met +PSI arm. An additional consent will be taken from the participant to undertake a semi structured, topic guided interview detailing their drug use and experiences whilst being on the trial (based on the ADAPT). This interview can take place at the same time as the week 24 visit or scheduled for a time convenient to the participant and interviewer. Participants will be reimbursed an additional £20 for their time in taking part in the interview. Researchers are to follow the EXPO PSI Interview Schedule as a topic guide, but the interview is designed to be semi structured. If a face-to-face interview is not possible, interviews can be recorded over the telephone; with the call on speaker and recorded using the audio recorder. When starting the interview, the participant should be reminded that the interview will be recorded, the length of time it may last, arrangements for payment and that they can withdraw from the interview at any time. Audio recordings should be recorded on trust approved audio recorders, the interviewer who conducted the interview is responsible for transcribing the interviews verbatim, naming the document with the participant number for the trial. Original audio file recordings are to remain at the site, securely stored electronically as per local

policy unless a Data Share Agreement is in place with the study sponsor. Transcripts with no personal identifiable information of the recordings will be sent to the study sponsor periodically upon request.

Extension Phase Interview. To be conducted at the South London and Newcastle sites with approx. 60 XR-Bup participants who consented to continue treatment after week 24 between 12-24 months of them being randomised in the trial. An additional consent will be taken from the participant to undertake a semi structured; topic guided interview (based on the OSTQOL) and additional assessment measures as outlined in section 9.2 of this protocol. If a UDS is not provided at the time of the interview, the most recent UDS taken within routine clinical care, up to 90 days prior to the interview date, can be recorded for trial purposes (consent permitting).

This interview can take place at a time convenient to the participant and interviewer. Participants will be reimbursed an additional £20 for their time in taking part in the interview. For the semi structured, topic guided section of the interview, researchers are to follow the EXPO Extension Phase Interview Schedule as a topic guide, but the interview is designed to be semi structured. If a face-to-face interview is not possible interviews can be recorded over the telephone; with the call on speaker and recorded using the audio recorder. When starting the interview, the participant should be reminded that the interview will be recorded, the length of time it may last, arrangements for payment and that they can withdraw from the interview at any time. Audio recordings should be recorded on trust approved audio recorders, the interviewer who conducted the interview is responsible for transcribing the interviews verbatim, naming the document with the participant number for the trial. Original audio file recordings are to remain at the site, securely stored electronically as per local policy unless a Data Share Agreement is in place with the study sponsor. Transcripts with no personal identifiable information of the recordings will be sent to the study sponsor periodically upon request.

9.2 Assessments by Study Week and Study Timeline

Measure	Baseline	Randomisation	Ongoing	Week 1	Week 2~	Week 4	Week 6~	Week 8	Week 10~	Week 12	Week 14~	Week 16	Week 18~	Week 20	Week 22~	Week 24	Withdrawal	Week 24 onwards	Ext. Phase Interview ++
Consent §	X																	X	X
Screening	X																		
UDS				X	X	X	X	X	X	X	X	X	X	X	X	X			
LFT *	X					X			X						X			X	
XR-Bup**			X	X		X	X		X	X		X	X					X	
Bup/Met **		X																	
ALC-QFM (TOP)***	X															X			
SCID-5-RV	X								X						X				X
ADAPT	X				X				X						X				
CGI-S	X																		
CGI-I						X			X						X				
CEQ-F – H***	X					X		X	X	X		X	X	X	X				
CEQ-F – C***	X					X		X	X	X	X		X	X	X				
VAS-N (H/C)***	X					X		X	X	X	X		X	X	X				
VAS-W (H/C)***	X					X		X	X	X	X		X	X	X				
DERS-SF	X					X			X						X				X
WSAS	X					X			X						X				
EQ-5D-5L	X								X						X				
AD-SUS	X									X					X				
KCF***						X			X						X				
QIDS-SR	X					X			X						X				
SURE								X		X					X				
PRO-S	X																		
PRO-I								X		X					X				
MoCA***	X									X									
OSTQOL																		X	
PHQ-4																		X	
PHQ-15																		X	
Exit Interview+																X			
Bup/Met + PSI Interview++															X				
TLFB	X	X																	X
Con Meds****		X				X				X					X			X	
Adverse Events Log		X																X	
Research Payments	X		X	X	X	X	X	X	X	X	X	X	X	X	X	X		X	
*****	20		10	10	10	5	10	10	10	5	10	10	5	10	10	10	5	10	20

§ screening to include pregnancy test, demographics and medical history. Participants receiving XR-Bup reconsented once at week 24 to continue receiving monthly injections;

* LFT for all participants at screening; during treatment for XR-Bup participants only under protocol;

** refer to section 6 of the protocol for guidelines;

*** used for mediation model;

**** ConMeds to be recorded continuously and reviewed at week 4, 12 and 24;

***** research payments are time offset to attend the clinic to complete research measures and cover travel (either a £20, £10, or £5 value, as detailed per visit applicable; loaded onto a prepaid card).

- + Exit Interview conducted at South London, Newcastle, West Midlands and Tayside sites with XR-Bup participants only. Participants will be reimbursed an additional £20 for their time in taking part in the interview (loaded onto a prepaid card).
- ++ Bup/Met +PSI Interview conducted at South London with Bup/Met +PSI participants only. Participants will be reimbursed an additional £20 for their time in taking part in the interview (loaded onto a prepaid card).
- +++ Extension Interview conducted at the South London and Newcastle sites with XR-Bup participants who consented to continue treatment after week 24 between 12-24 months of them being randomised in the trial.
- ~ Due to the Coronavirus 2019 (COVID-19) pandemic and to limit health care contacts, week 2, 6, 10, 14, 18 and 22 visits are permitted to be conducted via telephone if required. In this instance a UDS may not be obtained. Missed UDS due to visits being conducted by telephone are not considered a protocol deviation and do not have to be recorded on the deviations log however missed UDS for all other reasons should be recorded. All other visits are to be conducted in person at the study centre.

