6.6 Treatment discontinuation

A participant is discontinued from the study medications for any of the following reasons:

- Participant safety reasons, including adverse events (AEs) or significant concomitant illness, injury, or urgent surgeries/procedures that would, in the opinion of the Investigator, compromise treatment safety or deterioration in the patient's clinical condition.
- Participant request to discontinue study intervention. A participant is free to withdraw from study intervention at any time for any reason (they do not need to state a reason). Their participation is to be terminated upon his/her request, and the reason(s) for discontinuation appropriately documented.
- At the request of the Sponsor, regulatory agency, or Ethics Committee.
- Pregnancy. If not terminating, participant to discuss with clinician and continue with oral medication or withdraw following usual practice. Participants receiving IMP will not receive further injections and will receive oral medication or withdrawal according to usual practice.
- Administrative discharge due to non-adherence with site policies (e.g. violence towards other clients or staff).

In the event of an emergency, or if clinically indicated, a decision to surgically remove depot (up to 14 days from injection) may be made by the CI or PI, following discussion with the participant. An appropriately skilled medical practitioner may perform the surgical procedure, as follows:

1. Palpate the depot and surrounding area to confirm location.
2. Cleanse the area with an antiseptic solution.
3. Infiltration the area with local anaesthesia and wait for it to take effect.
4. Cover the area with sterile drape.
5. Incise the skin up to the subcutaneous tissues using a scalpel.
6. Using blunt and sharp dissection, identify the plane between the depot and surrounding subcutaneous tissues. Once the plane is identified, separate the superficial 25% of the circumference of the depot with blunt dissection.
7. Gently lift the incised ellipse of skin and depot with forceps.
8. Once the depot is removed, ensure haemostasis, and close the skin with non-absorbable sutures.

Removal of the depot is to be recorded as an Important Medical Event (IME).

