10.1 Primary efficacy parameter

With a 1-week measurement grace period from randomisation, the primary endpoint is the count of days abstinent from all non-medical opioids between days 8-168 (weeks 2-24; 161 days), combined with up to 12 urine samples for opioids providing biological verification of 36 of the 161 days in the outcome measure. If the UDS shows positive, the 3 days prior to the UDS will be reported as a positive and override what is reported on the timeline follow-back interview.

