10.3 Procedures for assessing efficacy parameters

Endpoint data collection will be gathered during 13 clinic visits using the TOP (timeline follow-back [TLFB] interview) and will also include recording of cocaine and non-medical benzodiazepines. All participants will be asked to provide a urine sample during each visit. If the participant does not take a UDS then all tested drugs will be taken to be positive for the past 3 days.

10.a Assessment of Cost Effectiveness

10.1a Primary Economic Parameter

The primary economic endpoint will be the incremental cost per quality-adjusted life year (QALY) gained of injectable depot maintenance buprenorphine versus standard oral therapy, adopting a broad societal cost perspective. Incremental costs will be determined from responses to the ADSUS questionnaire and the EXPO keyworker contact form. QALYs will be calculated from EQ-5D-5L scores and by applying the EQ-5D-3L crosswalk value set. This has no implications for the sample size calculation.

10.2a Secondary Economic Parameters

There will be 2 secondary economic parameters:

- (1) Health profiles (EQ-5D-5L);
- (2) Quantities of resource use (ADSUS) and total costs disaggregated by broad categories;

10.3a Procedures for assessing cost-effectiveness parameters

The cost utility analysis will consider patient QALYs and costs from a broad societal perspective including NHS and personal social services, productivity losses (including time off work because of illness), and criminal activity. This will be based on an incremental analysis of the mean costs and QALYs for injectable depot maintenance buprenorphine versus standard oral therapy.

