12.2 Statistical analysis

Assessment of Efficacy

The Statistical Analysis Plan (SAP) - approved by the trial committees - will be published on the Open Science Framework (www.osf.io) and summarised in the published trial protocol paper. After data lock in MACRO for each phase, the statistical analysis will be completed in Stata and R. Pooling data from all clinical treatment sites, a mixed-effects multivariable regression model for the primary analysis, with covariates (sex, age, drug injecting status, centre and baseline score on the outcome measure), and a site-varying random intercept. The medication preference factor will be explored for inclusion through interaction tests because it is expected that many participants have a medication preference given past or current exposure.

A maximum-likelihood multiple imputation approach will be used for the management of missing data with a sensitivity comparison to the complete case dataset. The cumulative distribution function of the primary endpoint will also be plotted for comparison purposes. Analyses of secondary outcomes will proceed using the same stratification and covariates as defined for the primary analysis model with linear (continuous outcomes) or logistic (binary or ordinal outcomes) regression framework. A causal mediation analysis (including craving, MoCa, and WSAS as mediators in separate models) will be implemented using a counterfactual framework to include a treatment/mediator interaction and covariates, based on univariable path screening, and with bias corrected bootstrapped estimates.

The clinical analysis will follow the intention-to-treat principle and include all patients in the group to which they are allocated. Alpha will be set at 5% for the primary and secondary outcomes (with associated 95% confidence intervals). The distributions of scale and count measures may be non-normal (skewed), so test statistics and effect sizes will be computed following appropriate transformation (e.g. natural log to obtain a geometric mean).

Assessment of Cost Effectiveness

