4.6 MISSING DATA

Primary and secondary count-based measures For the count-based measures two situations of missing are expected. Firstly, there will be those who have missing observations periodically through the study observation period but have remained in the study for these patients multiple imputation as described above will be adopted. The memory recall for the TLFB is 3 months therefore if a patient hasn't been to visits for a couple of months recall of up to 3 months is deemed reliable [4 - 6]. Where patients have gaps in their recall on the primary outcome (at most this would be 3 months) we would use the available data to impute for the patient. Sensitivity analysis will be conducted on this imputation using a best-case worst-case analysis, see section 6.9 for more details.

Secondly, there will be some cases of participants who completely drop out of the study during the observation period i.e. withdrawals or loss to follow ups. For these patients on the primary outcome and secondary count-based measures an offset (censoring) will be used to represent different exposures rather than multiple imputation.

Furthermore, some of the primary and secondary end points (TLFB) are based on self-report and UDS tests. Where data is available for self-report and UDS, if the results are inconsistent the UDS data will override the self-report, as indicated in section 5.2. Essentially where UDS is not available this does not result directly in missing data for the outcome as the self-report

will provide this data. However, the reliability of the self-report may be impacted therefore sensitivity analysis on missing UDS data will be conducted, see section 6.9 for more detail.

Continuous outcome measures

Missing observations are expected within the dataset. For missing items within an outcome measure, the published rules for completing missing data for the relevant measure will be applied. Where there are no missing data rules for the measure, if the number of missing items on an outcome is 20% or less, then the missing value for the item will be substituted by the individual's mean score for the remaining items on the scale (Bono, Ried, Kimberlin and Vogel 2007). If there are more than 20% missing items in the scale the outcome measure will not be calculated for the participant at that time point and multiple imputation methods will be used.

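### Protocol 6.6 and 8.3 end participation where 8.5 and the SAP's intention-to-treat set expect outcome data, and no section schedules follow-up after stopping

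*Protocol*

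**What the plan says.** - **Protocol 6.6** lists reasons for discontinuing study medication. Under participant request it speaks of leaving the study intervention and then says: "Their participation is to be terminated upon his/her request, and the reason(s) for discontinuation appropriately documented". The other four reasons, including administrative discharge, do not mention participation ending.
- **Protocol 8.3** asks for the first XR-Bup injection within 7 days of randomisation. Anyone who decides against it during the transition, or is judged unsuitable, leaves the trial. The sentence nevertheless labels them as ITT population.
- **Protocol 8.5** treats withdrawal from study drug as a separate matter from leaving the study. On leaving the study it asks for the timeline follow-back interview (TLFB), a urine drug screen (UDS) and craving measures. It adds: "Participants who wish to withdraw from EXPO will be asked to confirm whether they are still willing to provide data". It gives no timetable and no mode of contact.
- **Protocol 9.2 footnote**, introduced because of the pandemic, says "week 2, 6, 10, 14, 18 and 22 visits are permitted to be conducted via telephone if required", and then "All other visits are to be conducted in person at the study centre". Week 24 falls under the second sentence.
- **Protocol 10.1 and 10.3** set the primary window at days 8 to 168. "Endpoint data collection will be gathered during 13 clinic visits using the TOP".
- **Protocol 12.2**: "The clinical analysis will follow the intention-to-treat principle and include all patients in the group to which they are allocated". The analysis-set text in **SAP 3.1** likewise keeps every randomised participant as allocated, whatever treatment they received.
- **SAP 4.6** says of the interview that "recall of up to 3 months is deemed reliable". Gaps in people who stay in the study are filled by recall or imputed. For people who drop out completely, the remaining days are censored through an exposure offset.

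**The concern.** An intention-to-treat comparison of days abstinent needs drug use after treatment stops as well as before. If a site follows 6.6 and 8.3 literally, collection ends when treatment ends or fails to start. If it follows 8.5, collection may go on, but nobody is told when or how to make contact. The site's choice then decides which days enter the primary outcome.

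Two consequences follow. The 8.3 rule can operate only in the XR-Bup arm, so it can remove people from one side of the randomised comparison. For later dropouts the offset replaces unseen days with the person's own earlier rate. That is doubtful if abstinence changes once treatment stops.

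**Working it through.** **1. The window.** 168 − 8 + 1 = 161 days, as the protocol states.

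**2. The XR-Bup participant who never starts.** The first injection is due within 7 days and the window opens on day 8, so withdrawal under 8.3 can come before any primary day. The interview that 8.5 requests at withdrawal looks backwards and then contains no day from 8 onwards. Observed exposure is 0. With a log link and the usual offset of log(observed days), log(0) is undefined and the person leaves the model, despite the ITT label in 8.3 and the analysis set in SAP 3.1. In the oral arm, by contrast, protocol 6.7.2 handles three consecutive missed doses by re-starting through the clinic's induction procedure, with no mention of withdrawal.

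**3. Days lost by a later stopper, if nothing is collected afterwards.** Days lost = 168 − stop day.

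| Stop day | Days lost | Share of 161 |
|---|---|---|
| 28 | 140 | 87% |
| 84 | 84 | 52% |
| 140 | 28 | 17% |

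The documents give neither a number of stoppers nor their timing. Assume stop days uniform over days 8 to 168: the loss runs evenly from 160 to 0, mean 80. The share of all person-days lost is p × 80/161:

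- p = 15% (borrowed from the attrition inflation in SAP 4.1): 7.5%
- p = 25%: 12.4%
- p = 40%: 19.9%

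**4. What the offset does with those days.** Illustrative assumptions: abstinence while observed is 0.6 (oral) and 0.6 × 1.23 = 0.738 (XR-Bup); stoppers leave at mid-window; abstinence after stopping is q = 0.1 to 0.5 in both arms. The offset analysis returns 0.738/0.6 = 1.23 in every case. The full-window rate in an arm with observed rate r and stopping proportion p is r − (p/2)(r − q).

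| Stopping, XR-Bup vs oral | Offset ratio | Full-window ratio |
|---|---|---|
| 15% vs 15% | 1.23 | 1.22 to 1.23 |
| 25% vs 15% | 1.23 | 1.17 to 1.20 |
| 10% vs 30% | 1.23 | 1.24 to 1.35 |

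Example, second row, q = 0.1: (0.738 − 0.125 × 0.638)/(0.6 − 0.075 × 0.5) = 0.658/0.5625 = 1.17.

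**5. What the permitted telephone visits could recover.** Take 3 months as 90 days. A week-22 call (day 154) reaches back to day 154 − 90 + 1 = 65, so it covers days 65 to 154. A week-10 call (day 70) covers days 8 to 70. Together they cover days 8 to 154, which is 147 of 161 days (91%). Days 155 to 168 remain: 14 days. For someone who can be reached by telephone but will not attend, the in-person rule at week 24 costs at most those 14 days. If p = 15% all fall in this group, that is at most 0.15 × 14/161 = 1.3% of person-days.

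**The case against.** The strongest reply is that the documents do not treat stopping as leaving. In 6.6 participation ends only on request, and only under one of five reasons. Section 8.5 distinguishes the two kinds of withdrawal and asks for outcome data. Section 6.3 keeps a person in study treatment after a gap of more than 60 days. The SAP counts total days in medication to day 168 separately from time to first discontinuation, which implies observation past stopping, and its offset is reserved for complete dropouts. All of this stands. A reader might infer that the protocol merges stopping with leaving throughout; the documents do not support that. They show a conflict between 6.6 and 8.3 on one side and 8.5 and the SAP on the other.

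A reader might also infer that the in-person rule at week 24 is the main cause of lost days. Step 5 shows that it is not. What is missing is an instruction to contact people who have stopped.

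Third, an in-person week 24 protects urine verification, which is part of the primary endpoint. SAP 6.9 reports that screens had become monthly, with week 24 one of the six collection points. That is a fair reason not to offer telephone contact to people who would attend.

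Finally, no section says outright that the TLFB was taken by telephone. The 9.2 footnote permits telephone visits and mentions only the urine screen as possibly lost, so this is a reasonable inference and no more.

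**Conclusion.** The point holds as a conflict to reconcile and a gap to fill. The clearest exposure is the XR-Bup participant who never starts: under 8.3, if not followed, that person can have no primary days and drop out of a comparison described as intention-to-treat, with no counterpart in the oral arm.

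For later dropouts the size is conditional. An average loss of 80 of 161 days per stopper, and 7.5% of person-days at 15% stopping, rest on uniform stop days, no data after stopping, and a stopping proportion borrowed from the attrition allowance. A stopper who keeps attending loses nothing.

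A reader might infer that the primary result is biased in a known direction. The documents do not support this: with equal stopping the illustration barely moves, and otherwise the sign depends on which arm stops more. The change is worth making because it is cheap and because the offset cannot show what the unseen days contained.

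**What to change.** 1. Reconcile protocol 6.6 and 8.3 with 8.5. State that stopping, or never starting, study medication does not end outcome collection, which continues to day 168 unless the participant withdraws consent to data collection. This concerns data collection only and alters no treatment rule.
2. Schedule TLFB contacts for these participants in 9.2. Calls at weeks 10 and 22, both already permitted as telephone visits, cover days 8 to 154. Allow a telephone TLFB at week 24 only when the person will not attend in person, to cover the last 14 days. Everyone else keeps the in-person visit and its urine screen.
3. Flag these days so that the missing-UDS sensitivity analysis in SAP 6.9 includes them. Reconcile protocol 10.3, which counts a missing screen as 3 positive days, with SAP 4.6, which falls back on self-report. Until that is settled, each call without urine could be scored in two ways for 3 days.

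Cost: protocol and SAP wording, and up to three calls per person who stops and will not attend, using a contact route and interview already in use. The telephone days are self-report without urine verification, a weakness that SAP 4.6 already accepts when a screen is missing.
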